This study will include analysis to determine if therapy with oral divided-dose ACZ impacts global measures of clinical disability. Change in clinical disability measures assessed using the multiple sclerosis functional composite scale (MSFC) and the expanded disability status scale (EDSS) will be correlated with CBF, CBV and MTT. In addition, patient reported clinical outcome measures will be assessed at each time point. As this trial uses a small sample size, we would not expect statistically significant treatment effects on clinical disability though this exploratory measure should be useful in power calculation for the anticipated larger, randomized clinical trial.

Potential Risks and Benefits:

End Points - Efficacy

Altered cerebral perfusion has been previously reported in patients with MS. Global, regional and lesional changes in perfusion have been documented and some have found associations between decreased regional CBF and T2 lesion volume (Ota et al., 2013).

There are several currently approved treatments for MS that, in the aggregate, decrease the potential for formation of new MRI lesions. However, none have been clearly shown to impact the evolution of lesions, once formed. Several studies have shown that clinical disability correlates better with tissue integrity within black holes (Parry et al., 2002; Truyen et al., 1996; van Walderveen et al., 1999b). ACZ is a generally well tolerated therapy that has previously been shown to transiently increase cerebral perfusion. Long-term use of ACZ might more persistently improve global or regional CBF and could increase the proportion of lesions with improved tissue integrity.

End Points - Safety

ACZ is generally well tolerated with few reported adverse events (AEs). Transient perioral numbness has been reported in patients receiving bolus of IV ACZ. Hypersensitivity reactions, including diffuse pruritus, hives and shortness of breath have been reported with repeat administration of either IV or oral medication. A complete list of AEs is available in the package insert (see section 7) and will be provided to subjects with the informed consent.

Subjects will have face-to-face clinical evaluations at each scheduled visit (see section 4), will have monthly telephone or email contacts during the course of study and encouraged to report any AE occurring with drug at any point during the study. Any subject who is unable to tolerate study medication will be withdrawn from the study.

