During the dose escalation, in addition to issues of tolerability, subjects will be monitored at each transition point for the following specific serious AEs: paraesthesia, change in taste, accelerated change in blood pressure or fluid retention. Any subject with serious AEs will be withdrawn from the study. Patients with persistent serious AEs will be treated using standard medical practice.

STUDY POPULATION

List the number of subjects to be enrolled.

This exploratory study is designed to evaluate the long-term effects of oral ACZ on CBF in adult subjects with MS. We will enroll 100 MS subjects between the age of 18 and 55 without history of cerebrovascular disease or glaucoma.

There are several studies suggesting that MS lesions in the pediatric population differ from that typically seen in the adult population (Ghassemi et al., 2014; Renoux et al., 2007). To minimize potential confounding variables, all stages of the study will recruit only adult subjects with MS.

All subjects will be recruited from patients seen at the MS clinic located at the University of Texas Professional building (UTP) Neurology practice

Information about the study will be available on the UT Neurology web site and in print format at the UTP MS clinic.

Informed consent will be obtained from each participant prior to entry and, for subjects who elect to

participate in multiple parts of the study, prior to each stage.

Criteria for Recruitment

Subjects who wish to participate in either stage of the study will be evaluated by the principle investigator to determine if they meet inclusion and exclusion criteria. A thorough medical history will be performed to determine if any pre-existing cardiovascular disease or glaucoma is present. Subjects whose history is unknown will be encouraged to obtain evaluation by a primary care physician and eye-care specialist prior to recruitment. In addition, available blood tests, performed within six months of study entry, will be reviewed to determine if any renal or hepatic dysfunction is present.

Potential subjects with historical or laboratory evidence to suggest dysfunction in one of the above clinical systems will be excluded from study participation. As the rate of these comorbidities is low in a young population, we do not anticipate large numbers of failures at this stage of screening.

Inclusion Criteria

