b. Post Study Follow-up and Procedures

Subjects will be referred to their primary care physician for continued monitoring as directed should there be persistent adverse events from use of study drug.

c. Discontinuation Visit and Procedures

Subjects may withdraw from study for any reason and will not be replaced. Subjects who choose to withdraw from the study will be encouraged to complete the end-of-study visit.

Patients with intolerable paraesthesia, change in taste, accelerated change in blood pressure or fluid retention will be withdrawn from the study. Patients with persistent AEs will be referred to their primary care physician for continued monitoring and treatment using standard or care practices.

TRIAL MATERIALS

. Drug Substance: Intravenous Acetazolamide

Package Insert for Intravenous Acetazolamide: AcetaZOLAMIDE for Injection USP

For Intravenous Use.

Rx ONLY.

DESCRIPTION

Acetazolamide, an inhibitor of the enzyme carbonic anhydrase, is a white to faintly yellowish white crystalline, odorless powder, weakly acidic, very slightly soluble in water and slightly soluble in alcohol. The chemical name for acetazolamide is N-(5-Sulfamoyl-1,3,4-thiadiazol-2yl)-acetamide and has the following structural formula: M.W. 222.24 C4H6N4O3S2

Acetazolamide is available for intravenous use, and is supplied as a sterile powder requiring reconstitution. Each vial contains acetazolamide sodium equivalent to 500 mg of acetazolamide. The bulk solution is adjusted to pH 9.6 using sodium hydroxide and, if necessary, hydrochloric acid prior to lyophilization.

CLINICAL PHARMACOLOGY

Acetazolamide is a potent carbonic anhydrase inhibitor, effective in the control of fluid secretion (e.g., some types of glaucoma), in the treatment of certain convulsive disorders (e.g., epilepsy) and in the promotion of diuresis in instances of abnormal fluid retention (e.g., cardiac edema). Acetazolamide is not a mercurial diuretic. Rather, it is a nonbacteriostatic sulfonamide possessing a chemical structure and pharmacological activity distinctly different from the bacteriostatic sulfonamides.

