FDA approved extended release ACZ tablets from American Health will be used for "Treatment A". Commercially available placebo capsules manufactured by American Health composed entirely of lactose monohydrate filler that will be used for "Treatment B".

Study Drug Administration

"Treatment A" will be obtained directly from American Health and stored at MHHS pharmacy at Memorial Hermann Hospital. "Treatment B" is commercially available directly from American Health and will be shipped to MHHS pharmacy, shipped to CPHS pharmacy and stored. For stage 3, patients will be given either "Treatment A" or "Treatment B", based upon randomization, in sufficient quantities for each study visit. At the end of each study visit, patients will be asked to return any unused capsules. Unused capsules will be counted and stored in a secure facility at the McGovern Medical School, UTHealth.

Subjects with known hypersensitivity to sulfonamides or derivative drugs will be excluded from study participation (see section 3.4 for complete exclusion criteria). Subjects will be informed of common adverse reactions to sulfonamides including anaphylaxis, fever, rash (including erythema multiforme, Stevens-Johnson syndrome, toxic epidermal necrolysis), crystalluria, renal calculus, bone marrow depression, thrombocytopenic purpura, hemolytic anemia, leukopenia, pancytopenia and agranulocytosis. The drug will be discontinued and appropriate therapy instituted for any of these adverse reactions.

Specific Restrictions / Requirements

Subjects will be required to discontinue use of any frequently used over the counter medication, vitamin or other supplement one week prior to treatment with ACZ and for the duration of the study.

Blinding

Stage 1a to 2b are unblinded stages. Stage 3 is the only double-blinded portion of this study. Both subjects and raters will remain blinded to treatment randomization.Common AE such as paresthesias, particularly a "tingling" feeling in the extremities, and gastrointestinal disturbances such as nausea, vomiting and diarrhea typically occur early in treatment and might be more pronounced in subjects initially randomized to ACZ. Subjects will be encouraged to avoid disclosing any AE so as to maintain the blind for clinical rater(s). Imaging rater(s) will not have direct contact with study subjects and no potential for unblinding is present.

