Patients with intolerable paraesthesia, change in taste, accelerated change in blood pressure or fluid retention will be withdrawn from the study. Patients with persistent AEs will be referred to their primary care physician for continued monitoring and treatment using standard or care practices.

Concomitant therapy

Subjects will be encouraged to refrain from any over the counter medication, vitamin or other supplement including concomitant use of high-dose aspirin for analgesia. Subjects will be warned that an increased potential for serious AE has been reported in patients taking both ACZ and high-dose aspirin.

Subjects will be required, as stated in inclusion criteria (see section 3.3,) to be stable on any FDA-approved DMT.

SAFETY MEASUREMENTS

Definitions

The descriptions and grading scales found in the NCI Common Terminology Criteria for Adverse Events v 3.0 (CTCAE; published June 10, 2013) will be utilized for AE reporting.

Attribution of the AE:

- Definite The AE is clearly related to the study treatment
- Probable The AE is likely related to the study treatment
- Possible The AE may be related to the study treatment
- Unlikely The AE is doubtfully related to the study treatment
- Unrelated The AE is clearly NOT related to the study treatment

AEs should be recorded and graded 1 to 5 according to the CTCAE grades provided below:

- Grade 1 = Mild adverse event
- Grade 2 = Moderate adverse event
- Grade 3 = Severe and undesirable adverse event
- Grade 4 = Life-threatening or disabling adverse event
- Grade 5 = Death

For additional information, consult the National Cancer Institute's Common Terminology Criteria for Adverse Events v3.0 (published June 10, 2003) at the following URL: http://ctep.cancer.gov/reporting/ctc.html

An AE is defined as any untoward medical occurrence in a patient administered a pharmaceutical

product. Adverse events are to be recorded in the clinical chart. Severity, action taken, and relationship will be recorded as noted in the chart.

Serious Adverse Event (SAE) is defined as any untoward medical occurrence resulting in hospitalization or additional medical intervention in a patient administered a pharmaceutical product. SAE is to be recorded in the clinical chart. Severity, action taken, and relationship will be recorded as noted in the chart.

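### The Stage 1b dose-escalation rule labels paraesthesia and change in taste as serious adverse events requiring withdrawal, contradicting the protocol's own SAE definition, its list of common effects and its tolerability-based withdrawal rule

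*Combined protocol and SAP*

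**What the plan says.** The dose-escalation rule is under End Points - Safety in the combined protocol and SAP. It says that "in addition to issues of tolerability, subjects will be monitored at each transition point". What staff are to look for at those points is then given as a list, the "following specific serious AEs: paraesthesia, change in taste, accelerated change in blood pressure or fluid retention". The next sentence reads: "Any subject with serious AEs will be withdrawn from the study". A separate sentence in the paragraph before covers intolerance: "Any subject who is unable to tolerate study medication will be withdrawn from the study".

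Other sections bear on the same events:

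- **Safety Measurements, Definitions.** A serious adverse event is "any untoward medical occurrence resulting in hospitalization or additional medical intervention". The list of known effects in that section prints common ones in bold, and both paraesthesia and taste alteration are bold.
- **Discontinuation Visit and Procedures, and again at the end of Treatment, Blinding.** "Patients with intolerable paraesthesia, change in taste, accelerated change in blood pressure or fluid retention will be withdrawn from the study". The word serious is not used in either place.
- **Treatment, Blinding.** This speaks of "Common AE such as paresthesias" and says that such effects "typically occur early in treatment".
- **Safety Monitoring Plan.** The team reports no serious event in its own experience with IV or oral acetazolamide and expects none in this trial. AEs are to be documented by frequency and grade, with treatment adjusted or stopped as needed.
- **Oral package insert, Precautions.** A higher dose may raise the incidence of paraesthesia.

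**The concern.** The escalation rule makes two named symptoms serious in themselves. The SAE definition depends on outcome, and tingling or altered taste does not meet it without hospitalization or intervention. Site staff therefore have two incompatible tests for the same event: one for classifying it and one for deciding whether the subject leaves.

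What is at stake is retention in Stage 1b. This stage measures the change in cerebral blood flow (CBF) at each oral dose, up to 4000 mg per day. It has up to 10 subjects, and Subject Replacement says that those who withdraw are not replaced. Paraesthesia is an expected effect here, and the label says it may become more frequent as the dose rises. A literal reading would remove subjects for it even when they tolerate it well, and the upper dose steps would be measured only in those who had no such event lower down. Serious-event counts would also be inflated with events that the protocol elsewhere treats as ordinary.

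**Working it through.** The plan states no figure on this point, so the check is a comparison of texts followed by a count from the schedule.

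**1. Paraesthesia and change in taste under each section**

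| Section | Status of the event | Trigger for withdrawal |
|---|---|---|
| End Points - Safety (dose escalation) | Both named as serious | Occurrence; no grade or tolerability condition |
| Definitions | Serious only by outcome; both listed as common | None stated |
| Discontinuation Visit; Blinding | Not called serious | Intolerable paraesthesia; for taste the qualifier may or may not carry over |
| Safety Monitoring Plan | No serious events seen or expected | Adjust or stop as needed, by frequency and grade |

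The first row conflicts with the second on classification, for both events. It conflicts with the third on the trigger. That conflict is firm for paraesthesia and less certain for taste, because intolerable may grammatically govern only the first item in the list. Neither section says that intolerability is the only ground for withdrawal.

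**2. Is the escalation rule just the tolerability rule restated?** No. It is introduced as additional to tolerability, and intolerance already leads to withdrawal under the sentence before it. As written, it is a further ground.

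**3. Scans forfeited per subject.** Under Study Visits and Procedures, each scan is taken before the next dose begins. A subject withdrawn at a transition visit can therefore still supply the scan for the dose just completed. With D doses and withdrawal at transition k, scans lost = D − k.

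- Trial Schedule table (500, 1000, 1500 and 2000 mg BID), D = 4: k = 1 loses 4 − 1 = 3; k = 2 loses 2; k = 3 loses 1; k = 4 loses 0.
- Visit text (starting at 250 mg BID), D = 5: k = 1 loses 5 − 1 = 4; k = 2 loses 3; k = 3 loses 2; k = 4 loses 1; k = 5 loses 0.

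The loss is always at the later, higher doses. The remark in Blinding that such effects come early points towards k = 1. The package insert points towards further cases as the dose rises.

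**4. Number of subjects affected.** This cannot be computed. The documents give no incidence for either event. The relevant number is also only the tolerable cases, because intolerant subjects leave in any event.

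**The case against.** The strongest reply is that the authors cannot have meant ordinary tingling. They report no serious events with a drug whose common effects they list as including paraesthesia, which makes sense only if ordinary paraesthesia is not counted as serious. The same four events appear in the same order in two other sections, introduced by intolerable, and the treating physician grades every AE. On this view the escalation rule means serious instances of these events, and only a word is wrong.

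As an account of intent, this is plausible. It is not what the text says: the rule names the events themselves and sets them apart from tolerability. The intolerable wording also sits after the Stage 3 visits and within the Blinding text, so its reach to Stage 1b is likely but not explicit.

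A second reply is that strict stopping is a reasonable choice in a small unblinded stage that goes to 4000 mg per day, when the labelled glaucoma dose is 1 g per day. That has force for blood pressure change and fluid retention, and the fix leaves those stops in place. It has less force for two effects that the protocol itself lists as common.

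A reader might also infer a definite loss of precision in the dose-step CBF estimates. The documents do not support one. Any such figure needs a withdrawal count that they do not give and a standard deviation for Stage 1b change. The 30% in Sample Size and Statistical Methods is for the Stage 3 comparison with placebo.

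**Conclusion.** The rule is wrong as written, and the point should be corrected. The classification conflict is clear for both events. The conflict over the withdrawal trigger is clear for paraesthesia and probable for taste. The cause is most likely loose drafting.

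The effect is confined to safety classification and to retention in Stage 1b. For an individual subject it ranges from no scan lost to 3 of 4 (table) or 4 of 5 (text). This assumes withdrawal at a transition visit with that visit's scan obtained. The total over the stage is unknown.

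Two wider readings should be resisted. A reader might infer that Stage 3 is compromised, but its sample size and primary analysis do not depend on this rule, and the later doses are largely named already. A reader might also infer that all four listed events are wrongly treated as grounds for withdrawal. The documents do not list accelerated blood pressure change or fluid retention as common, so for those two only the label is at issue.

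The documents do not say whether Stage 1b is complete. If it is, what remains is consistent classification and a clear account of any withdrawals.

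**What to change.** 1. **End Points - Safety.** Replace the phrase specific serious AEs with *specific AEs of interest*. State that paraesthesia or change in taste leads to withdrawal only if it is intolerable or meets the SAE definition in Safety Measurements.
2. **Same paragraph.** Keep withdrawal for accelerated blood pressure change and for fluid retention as it stands, but do not call either an SAE unless it meets that definition.
3. **Discontinuation Visit and Procedures, and Blinding.** Reword both to match, so that the qualifier clearly covers both symptoms: *paraesthesia or taste change, if intolerable; accelerated blood pressure change; or fluid retention*. Amending only the escalation rule could leave these sections withdrawing subjects for any change in taste.

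The cost is amendment wording. No visit, scan or sample size changes. The downside is a slightly less conservative stop for two non-serious effects. Withdrawals for intolerance will continue and will still select subjects, so the fix reduces the loss at higher doses but does not remove it. If intolerable was meant to govern all four events in item 3, the new wording is stricter for blood pressure change and fluid retention, which errs on the side of safety. The sponsor should confirm that.
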